15.1	
 • Modified the schedule for Visit 1. • Modified the schedule for Visit 2: Randomization to include the following notation: “If shipping of study agent to the study site will be required, subjects should be randomized at least 3 days prior to treatment start to ensure study agent availability.” • Modified the visit window for Visit 8 and 16 from +1 Day to +3 Days. • Modified the schedule for Visits 3-8 and 11-16 to include supine and standing blood pressure measurements with notations re: timing of measurements. 	
 • Added screening for orthostatic hypotension and supine hypertension. • Added to provide clarification and ensure availability of study agent/placebo at study site for eligible subjects. • Visit windows extended so a weekend follow-up visit is not required (patient can be discharged, and the visit can occur on a Monday). • Increased safety monitoring.

Protocol Version 2.1 dated 10AUG2018
Replaces: Protocol Version 2.0 dated 19JUL2018

Location	Description	Purpose
Throughout	
Protocol version previously read: V2.0_19JUL2018
 
Now reads: V2.1 10AUG2018
	Version Control
7.3.5	
Modified the schedule for Visits 8, 9, 16, and 17 as follows:
 
 • MoCA moved from Visits 8 and 16 to Visits 9 and 17. 	MoCA testing was shifted to avoid potential data redundancies and complications of administration during the same visit as the D-KEFS and dCDT evaluations.

Location	Description	Purpose
15.1	Modified the schedule for Visits 8, 9, 16, and 17 as follows: 
 MoCA moved from Visits 8 and 16 to Visits 9 and 17. 	MoCA testing was shifted to avoid potential data redundancies and complications of administration during the same visit as the D-KEFS and dCDT evaluations.

Protocol Version 2.0 dated 19JUL2018
Replaces: Protocol Version 1.1 dated 04JUN2018

Location	Description	Purpose
Throughout	Protocol version previously read: V1.1_04JUN2018 Now reads: V2.0 19JUL2018	Version Control
Throughout	Grammar and style changes	For protocol clarity and standardization
List of Abbreviations	The following abbreviations have been added: 
 AD: Alzheimer’s disease ASL MRI: Arterial-spin Labeling magnetic resonance imaging BP: Blood pressure CRA: Clinical research associate tf-MRI: Task-free functional magnetic resonance imaging WOCBP: Women of childbearing potential 	Updated the list of abbreviations to reflect abbreviations used in the body of the protocol
List of Definitions Infusion Nurse	Sentence Previously Read: The unblinded study personnel, [...] responsible for administering the investigational product. The Infusion Nurse ensures the investigational product is administered at the correct infusion rate and appropriate blinding techniques are used to prevent inadvertent unblinding of study staff and study subjects during and immediately following the infusion period. Sentence Now Reads: The unblinded study personnel, [...] responsible for administering the	Updated for clarity to reflect the placebo-controlled design

Location	Description	Purpose
	investigational product/placebo. The Infusion Nurse ensures that the investigational product (GRF6021)/placebo is allocated appropriately, administered at the correct infusion rate, and appropriate blinding techniques are used to prevent inadvertent unblinding of study staff and study subjects during and immediately following the Infusion Period.	
List of Definitions Infusion Time	List of Definitions Infusion Time is now Infusion Period	For protocol clarity and standardization
Schematic of Study Design	Inpatient Treatment 2 Follow up Visit was incorrectly listed as Day 6. Changed to Day 90 to reflect the Schedule of Events.	Correct typographic error in Schematic of Study Design
2.2, 2.3	Removed “young” as a descriptor of the donor pool for manufacturing GRF6021.	To more accurately reflect the donor pool
3	Modified description of exploratory objectives as follows: Sentence previously read: In addition, brain imaging (MRI) will be conducted in consenting patients to identify potential indicators of PD MCI and PDD progression, as well as potential therapeutic effects of GRF6021. Sentence Now Reads: In addition, magnetic resonance imaging (MRI) of the brain will be conducted after the second treatment period in consenting subjects to identify potential therapeutic effects of GRF6021.	For protocol clarity and standardization
4.1	Updated the Description of the Study Design to more accurately reflect the Schedule of Events and clarify the additional, optional MRI.	For protocol clarity and standardization
4.2.3	Added details to the Exploratory Endpoints regarding the endpoints that may be evaluated using the second MRI obtained from consenting subjects.	For protocol clarity
5.1	Amended Inclusion Criteria as follows: 
 • #4: Clarified that the MoCA score required for inclusion is 13-25, inclusive • #11: Clarified that the systolic ejection fraction required for inclusion is greater than 	#4, 11: For protocol clarity and standardization #13: Removed “serum” pregnancy testing, as urine pregnancy testing may be performed at Visits 3 and 11

Location	Description	Purpose
	or equal to 55% 
 #13: Removed specification for “serum” pregnancy testing 	
5.2	Amended Exclusion Criteria as follows: 
 #14: Removed “The trial partner should understand the nature of the study and be willing to complete the trial partner scales and functional assessments throughout the study.” #18: Added that concurrent participation in any other therapeutic treatment trial is exclusionary to align with Section 7.5 Prohibited Medications, Treatments, and Procedures 	#14: It is not anticipated that the trial partner will be expected to complete any scales or functional assessments as part of this study. #18: For protocol clarity and standardization
5.4.1, 8.4.1	Clarified the investigator’s responsibilities for following Adverse Events (AEs). AEs will be followed until resolution or deemed stable, unless the subject is lost to follow up.	For protocol clarity, standardization, and alignment with the study’s safety management plan (in draft)
5.4.2, 7.3.7	Clarified that only subjects who have received at least one infusion but are withdrawn or withdraw from the study early will be encouraged to complete the End of Study Visit procedures.	Clarification
7.1.1.1	Added the Hoehn and Yahr scale as part of the assessment of PD to the list of Screening procedures.	For protocol clarity and standardization, as Hoehn and Yahr is required for assessment of eligibility
7.1.1.1.1	Removed schedule for administering the Sheehan-Suicidality Tracking Scale (S-STSS), as this information is specified in Section 7.3 Study Schedule and Section 15 Schedule of Events.	For protocol standardization.
7.1.1.1.2, 7.3.1	Added that “The stage of the disease will be classified using the Hoehn and Yahr scale” as part of the assessment of PD and cognitive impairment and other minor edits.	For consistency with Section 5.1 Inclusion Criteria
7.1.1.1.5	
Previously read: Information pertaining to the subject’s socioeconomic status (e.g. highest level of income achieved, education, longest held occupation), ethnicity, race, marital status, and family size will be collected by interview with the subject and the subject’s trial partner at screening.
 
Now reads: Demographic information such as the subject’s education level, ethnicity, and race will be
	To clarify the types of demographic data that may be collected

Location	Description	Purpose
	collected by interview with the subject and the subject's trial partner at screening.	
7.1.1.8	Added a more detailed description of the neurological exam.	To specify required assessments to be performed as part of the neurological examination
7.1.1.1.10	Removed upper limit of systolic ejection fraction, as this was inconsistent with Section 5.1 Inclusion Criteria.	For protocol clarity and standardization
7.1.1.1.12	Removed description of the Visit 16 MRI from the description of the MRI required for screening.	For protocol clarity and standardization. A detailed description of MRI procedures is provided in Section 7.2.2.2.
7.1.1.2.7	Clarified that only the physical exam and weight measurements (not height) will be repeated at the End of Study Visit.	To align with the updated Schedule of Events
7.1.1.3.2	Added that "Subjects will have two CDR-CCB trainings during the screening period to ensure adequate performance at the Baseline Visit."	For protocol clarity and alignment with the Study Schedule
7.1.1.3.5	Specified that only Parts 1-3 of the MDS-UPDRS will be completed for this study.	Clarification
7.1.1.3.9	Provided further guidance regarding administration of the GDS-15.	For protocol clarity
7.2.2.1	Modified to state that DNA for ApoE analysis will be obtained from a blood serum sample.	Clarification
7.2.2.2	Updated to more accurately reflect the processes for MR image acquisition and interpretation as well as describe the exploratory endpoints that may be assessed using MR images obtained from consenting subjects.	Clarification
7.2.3	Removed reference to laboratory addendum.	An addendum to the lab manual is not required. A lab manual will be developed and distributed to sites that includes instructions for collecting and processing all specimens (standard, non-standard, and specialty).
7.3.2, 7.3.6, 15	Removed option for splitting Baseline and End of Study Visits.	It is expected that all required Baseline and End of Study activities may be completed in a single visit.
7.3.2, 7.3.4, 15	Amended the schedule for collecting samples for proteomics/epigenetics/biobanking and ApoE testing, such that no samples will be collected	The proteomics/ epigenetics/ biobanking samples collected during Visit 3 are sufficient for baseline. The

Location	Description	Purpose
	during the Baseline Visit and the sample for ApoE will be obtained during Visit 3.	Visit for collecting ApoE was changed to reduce the number of required blood draws.
7.3.3	Clarified that subjects will be randomized at the conclusion of Visit 2 after eligibility has been confirmed (including MRI and echocardiography results).	Clarification
7.3.4, 15	Added a \pm 7-day visit window for Day 85.	To aid protocol feasibility
7.3.5, 15	Modified the schedule for Follow-up Visits as follows: 
 • PDQ-39 moved from Visit 8 to Visit 9. • Added a \pm 7-day visit window for the optional MRI at Visit 16. 	To allow for a greater window between collection timepoints for the PDQ-39 Added the MRI visit window to aid protocol feasibility
7.5	
Previously read: Concurrent participation in any other therapeutic treatment trial. If there was prior clinical trial participation, then the last dose of the investigational agent for symptomatic therapies must have been at least 30 days for small molecules, 4 months for disease modifying therapies, and 1 year for vaccine or immunotherapy trials prior to screening.
 
Now reads: Concurrent participation in any other therapeutic treatment trial. If there was prior clinical trial participation, subject must have discontinued investigational agents for at least 30 days for small molecules, and 1 year for active or passive immunotherapies prior to screening.
	For protocol clarity and alignment with the Inclusion/Exclusion Criteria
8.2.2	Modified to reflect that if either the investigator or the Sponsor considers an AE related, then the event will be considered related for reporting purposes.	To align with the study's safety management plan (in draft) and processes
8.2.3	Previously read: The investigator will be initially responsible for determining whether an AE is expected or unexpected.	To align with the study's safety management plan (in draft) and processes

Location	Description	Purpose
	Now reads: The Sponsor or designee will be responsible for determining whether an AE is expected or unexpected.	
8.4.2.1, 8.4.2.2	Modified the timeframes for reporting SAEs and provided additional instructions for SAE reporting.	For protocol clarity and alignment with safety management processes and procedures.
8.4.3	Provided additional details and guidance on reporting AEs of Special Interest.	Clarification.
8.4.4	Provided additional details and guidance on reporting of pregnancy.	For protocol clarity and alignment with safety management processes and procedures.
8.5	Updated the Study Halting Rules to reflect that dosing may be temporarily halted if a Safety Evaluation Meeting is triggered. The decision to temporarily halt dosing will be based on the safety observations.	Clarification.
10.4.7	Updated to include additional information regarding the Planned Interim Analysis.	Clarification.
10.6.1	Removed mixed block size specifications.	Information is not relevant to the protocol.
12.5	Added that “Subjects may choose whether the Sponsor can store and use samples for further research.”	To align with the informed consent form.
15.1	Updated the Schedule of Events Table to reflect revised Study Schedule and provided additional details/clarification in the footnotes.	For protocol clarity and standardization.

Protocol Version 1.1 dated 04JUN2018

Replaces: Protocol Version 1.0 dated 01MAY2018

In this table, changes from Version 1.0 dated 01MAY2018 are described and their rationale is given.

Location	Description	Purpose
Throughout	Update of study design to 90 subjects who will be randomized in a 2:1 ratio to active treatment (approximately 60 subjects) or placebo (approximately 30 subjects). Subjects will receive one infusion per	Updated study design

Location	Description	Purpose
	day of active or placebo treatment for 5 consecutive days during week 1 and week 13.	
Throughout	Protocol version previously read: V1.0_01MAY2018 Now reads: V1.1_04JUN2018	Version Control
Throughout	Grammar and style changes	For protocol clarity and standardization
Throughout	Optional cerebrospinal fluid biomarker research was removed.	Removed for safety considerations
Throughout	Secondary endpoint added: Change from baseline in Delis-Kaplan Executive Function System (D-KEFS) Verbal Fluency.	Test provides auxiliary information regarding verbal fluency to the CDR-CCB, which does not include assessments in this critical cognitive domain
List of Abbreviations	Removed CSF: Cerebrospinal Fluid and added D-KEFS: Delis-Kaplan Executive Function System.	CSF biomarker was removed and D-KEFS test was added
Schematic of Study Design	Schematic updated to reflect new study design.	Updated study design
Section 2.2	Provided additional content regarding an allometric scaling model for conversion of preclinical to clinical dosing volumes, as well as alternative models, including isometric scaling. Using isometric scaling based on blood volume provides an equivalent human dose of 413 mL. A table (Table 1) with detailed information is included.	Provided clarification of the dosing volume calculations
Section 7.1.1.3.3	Previously: Digital Clock Drawing Test (with accompanying descriptive information). Now: Delis-Kaplan Executive Function System (with accompanying descriptive information).	Section added for description of D-KEFS test
Sections 7.1.1.3.4-7.1.1.3.9	Previously: Sections 7.1.1.3.3 – 7.1.1.3.8. Now: Sections 7.1.1.3.4 – 7.1.1.3.9.	Sections renumbered to accommodate new section for D-KEFS test.
7.2.1	Added the following sentence to the first paragraph: “The total blood volume collected for each subject during Visits 1-19 is approximately 465 mL.”	Provide clarification regarding total blood volume collected during the study.

Location	Description	Purpose
Section 7.2.2.4	Section for Cerebrospinal Fluid Biomarker Collection was removed.	Removed for safety considerations
Section 7.3.5	MRI Assessment removed from Visit 10 and added to Visit 16.	Due to new study design there will be no crossover (placebo to active), so this timing for MRI investigation is more appropriate
Section 10.5	
Sentence previously read: In a sample of 45 subjects, the upper bound of the 95% confidence interval for the frequency of an unobserved AE is approximately 7%.
 
Sentence now reads: In a sample of 60 subjects, the upper bound of the 95% confidence interval for the frequency of an unobserved AE is approximately 5%.
	Correction for new sample size for 2:1 randomization ratio
Section 15.1	Updated Schedule of Events Table: removed CSF/lumbar puncture and added D-KEFS.	Removed CSF biomarker for safety considerations; D-KEFS test added
Section 16.1	Added three new references (Delis 2001, Delis 2004, Emre 2004).	Added in support of D-KEFS test

			would be listed. Stated shifts from baseline in coagulation and quantitative urinalysis parameters will also be provided.
2.0	21-May-2019	9.3	Clarified the visits in which orthostatic vital signs will be presented pre- and post-infusion. Clarified the position of abnormal vital signs and added criterion of orthostatic hypotension. Included reference to the blood pressures of special interest that will be summarized separately.
2.0	21-May-2019	10	Stated that BPSIs were identified and summarized in the SAP, but are not in the current protocol version.
2.0	21-May-2019	11.1	Clarified the Hoehn and Yahr will be used, not the modified Hoehn and Yahr.
2.0	21-May-2019	11.3	Added a subsection to detail the echocardiogram results that will be listed.
2.0	21-May-2019	13.1	Indicated which demographic and safety TFLs will also be provided at the efficacy IA.

2.0	21-May-2019	14.2	
Updated footnotes, titles, and table shell formatting for consistency with text and other shells.
 
Added a table of AEs with terms associated with blood pressure changes.
 
Added summary and shift tables of coagulation and quantitative urinalysisf laboratory parameters.
 
Added a table of blood pressure values of special interest.

2.0	21-May-2019	14.3	
Added listings of coagulation, immunology, and serology laboratory parameters.
 
Added a column to the protocol deviations listing to indicate which deviations exclude someone from the Per Protocol analysis Set.

3.0	01-May-2020	8.3.2	
Added subsections for Volumetric MRI, Resting fMRI, and ASL MRI describing what tests, locations and laterality will be presented.

3.0	01-May-2020	13.2	
Removed the 'X' from ANCOVA tables as they were not provided

			and the interim efficacy analysis
3.0	01-May-2020	14.2	Added table shells for Volumetric MRI and ASL MRI
3.0	01-May-2020	14.3	Added listing shells for Volumetric MRI and ASL MRI
3.0	01-May-2020	14.4	Added figure shells for the individual MDS-UPDRS scores (Part 1, Part 2, and Part 3)
4.0	17-Aug-2020	5	Refined Per Protocol set definition, Added Complete population
4.0	17-Aug-2020	7.1	Added description of subjects who did not complete the study due to COVID-19
4.0	17-Aug-2020	9.1.1	Added derived action taken variable for AEs
4.0	17-Aug-2020	13	Added medical history table by LLT, added efficacy tables in the Complete Set

The structure and content of this SAP provides sufficient detail to meet the requirements identified by the Food and Drug Administration (FDA), European Medicines Agency (EMA), and International Conference on Harmonization (ICH) of Technical Requirements for Registration of Pharmaceuticals for Human Use: Guidance on Statistical Principles in Clinical Trials¹ All work planned and reported for this SAP will follow internationally accepted guidelines, published by the American Statistical Association² and the Royal Statistical Society³, for statistical practice.

The planned analyses identified in this SAP may be included in clinical study reports (CSRs), regulatory submissions, or future manuscripts. Also, post-hoc exploratory analyses not necessarily identified in this SAP may be performed to further examine study data. Any post-hoc or unplanned, exploratory analysis performed will be clearly identified as such in the final CSR.

The statistical plan described hereafter is an *a priori* plan. It will be submitted to file prior to any unblinded inferential or descriptive analysis of data pertaining to Alkahest's study ALK6021-201.

2. Study Objectives and Endpoints

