10.4.7 PLANNED INTERIM ANALYSES

An unblinded interim analysis of the safety endpoints, including the primary endpoint and secondary safety endpoints, was conducted when approximately 20 subjects completed Visit 8 (end of first dosing period). The requirement that subjects remain on an inpatient unit during each treatment period was included in the

protocol to enable safety monitoring during dosing. The Sponsor reviewed the safety data from this interim analysis to assess whether the need for inpatient stays during dosing should remain a requirement. The unblinded safety analysis was performed following a data-cut on 09JUN2019 and included 32 subjects. Based on the results of the interim safety analysis and feedback from FDA, the inpatient requirement is no longer required as reflected in this version of the Protocol.

An unblinded interim analysis of the MoCA, CDR-CCB, and MDS-UPDRS3 secondary efficacy endpoints is planned when approximately 40 subjects have completed Visit 8 (end of first dosing period). As the study is not powered for efficacy and no decisions will be made regarding stopping the trial, statistical testing will be performed at the 0.05 level using two-tailed tests on both the Evaluable and Per Protocol datasets. To minimize potential bias of the remaining efficacy and safety data, only aggregated summary tables will be provided.

Safety will be monitored on an ongoing basis. If a Safety Evaluation Meeting is triggered (see [Section 8.5](#)), an ad hoc interim safety analysis will be performed. If such an ad hoc safety interim analysis is conducted, the treatment assignment will remain masked, unless unblinding is deemed necessary by the Sponsor for safety evaluation.

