Aside from designated personnel whose sole responsibility necessitates access to unblinding information (e.g., the unblinded CRA whose sole responsibility is to ensure study agent/placebo accountability, the unblinded clinical supply manager, etc.), the Sponsor and their representatives will be blinded with respect to subjects' treatment allocation through database lock unless breaking the blind is required for safety reasons (see [10.6.3 Breaking the Study Blind/Subject Code](#)). The unblinded interim analyses will be performed by unblinded statisticians who are not members of the protocol study team. The data will be provided in aggregate fashion so the difference between study agent and placebo is compared but individual treatment allocation remains blinded.

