10.3	
 • The safety dataset includes all subjects who received any amount of the study agent as opposed to “at least one dose.” • In the description of the evaluable dataset, added the following text, “have a diagnosis of PD and cognitive impairment per the inclusion criteria” 	
Since the IMP is administered by IV infusion, subjects who receive any volume of IMP will be considered part of the safety dataset.
 
Revised to ensure that only subjects who have a diagnosis of PD and cognitive impairment are included in the evaluable dataset.

10.4.7	Updated to include the outcome of the interim safety analysis.	Updated since the planned interim safety analysis was completed in June 2019.
13.1	Previously read: For each subject who receives the study agent, the eCRF must be completed [...]	Revised for clarity, as screen failure data is captured in the eCRF.

	Now reads: For each subject enrolled in the study, the eCRF must be completed [...]	
13.3	Major and Minor Protocol Deviation content updated.	Updated to reflect revised Alkahest Standard Operating Procedures related to Major and Minor Protocol Deviations.

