4.2. Interim Analysis and Data Monitoring

An unblinded interim analysis of the safety endpoints, including the primary endpoint and secondary safety endpoints, is planned when approximately 20 subjects have completed Visit 8 (end of first dosing period). The requirement that subjects remain in an inpatient unit during each dosing period was included in the protocol to enable safety monitoring during dosing. Once the Sponsor has reviewed the safety data from this interim analysis, the need for inpatient stays during dosing will be reassessed.

An unblinded interim analysis of the MoCA, CDR-CCB, and MDS-UPDRS Part 3 secondary efficacy endpoints is planned when approximately 40 subjects have completed Visit 8 (end of first dosing period). As the study is not powered for efficacy and no decisions will be made regarding stopping the trial, statistical testing will be performed at the 0.05 level using two-tailed tests on both the Evaluable and Per Protocol sets. To minimize potential bias of the remaining efficacy and safety data, only aggregated summary tables will be provided. The data will be provided in aggregate fashion so the difference between study agent and placebo is compared but individual treatment allocation remains blinded. An independent statistician other than the author of this plan will perform the unblinded analysis.

Safety will be monitored on an ongoing basis. If safety events of potential concern occur during the trial (i.e., 3 related events in the same SOC or a suspicious overall pattern), a Safety Evaluation Meeting will be triggered and an ad hoc interim safety analysis will be performed. Dosing may be temporarily halted based on the observations. The purpose of the meeting is for investigators, the Sponsor, external consultants with expertise relevant to the specific safety signal(s) detected as necessary, and the contract research organization (CRO) Medical Monitor(s) to discuss and evaluate the safety of the subjects using available aggregated safety data and without compromising study blinding, unless the Sponsor deems unblinding necessary for safety evaluation.

The results that will be presented for each interim analysis are flagged in the table of contents.

A separate analysis plan will be prepared for the CDR-CCB endpoints.

5. Analysis Sets

The following analysis sets are planned for this study:

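### SAP v4.0 still calls itself an a priori plan filed before any unblinded analysis, yet its refined Per Protocol Set and new Complete Set post-date the unblinded safety interim and probably the efficacy interim

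*SAP*

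**What the plan says.** SAP Section 1 (Overview) opens its timing claim with "The statistical plan described hereafter is an" a priori plan, and continues: "It will be submitted to file prior to any unblinded inferential or descriptive analysis of data". The same section promises that post-hoc or unplanned analyses will be identified as such in the clinical study report.

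The SAP Document History records, for v4.0 of 17-Aug-2020, Section 5: "Refined Per Protocol set definition, Added Complete population".

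Protocol 10.4.7 reports: "The unblinded safety analysis was performed following a data-cut on 09JUN2019 and included 32 subjects". It adds: "The Sponsor reviewed the safety data from this interim analysis to assess whether the need for inpatient stays during dosing should remain a requirement". Protocol 18.1 gives the reason for revising that section: "Updated since the planned interim safety analysis was completed in June 2019". On what interim output looks like, Protocol 10.6.1 says: "The data will be provided in aggregate fashion so the difference between study agent and placebo is compared", with individual allocation remaining blinded.

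SAP Section 4.2 still writes both interims in the future tense. The efficacy interim, for example, "is planned when approximately 40 subjects have completed Visit 8 (end of first dosing period"). SAP Section 10 (Changes from Planned Analysis) mentions only the blood-pressure criteria.

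**The concern.** The Section 1 claim covers any unblinded analysis, descriptive ones included, so one completed unblinded interim before the version date is enough to make it untrue. What changed in v4.0 is the membership of two of the three efficacy sets. Both sets select on events after randomization: doses received, visits completed in window, deviations and, for the Complete Set, changes in medication. Results in such sets can move with the definition, so it matters whether the definition was fixed before or after by-arm results existed.

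Followed as written, the plan would report results from both sets under the a priori label, outside the promise to flag post-hoc work. Because the SAP makes no multiplicity adjustment (Section 6.1.3), correct labelling is the main guide to how much weight those p-values can bear.

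**Working it through.** This is a question of the order of events, so the check sets dates side by side and then counts tables.

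**Dates, relative to the 09JUN2019 safety data cut (Protocol 10.4.7)**

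| Event | Date | Days from cut |
|---|---|---|
| SAP v2.0 | 21-May-2019 | −19 |
| Protocol v5.0 | 23SEP2019 | +106 |
| SAP v3.0 | 01-May-2020 | +327 |
| SAP v4.0 | 17-Aug-2020 | +435 |

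SAP v4.0 follows v3.0 by 435 − 327 = 108 days.

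**Safety interim.** It was unblinded, completed in June 2019 and reviewed by the sponsor. SAP Table 4 flags adverse-event, laboratory and vital-sign tables by treatment for it. This alone contradicts the Section 1 sentence for v3.0 and v4.0.

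**Efficacy interim.** No date or actual sample size is given. The v3.0 history entry for Section 13.2 removes the interim flag from the ANCOVA tables on the ground that they were not provided, and goes on to name the interim efficacy analysis. The past tense makes it probable, not certain, that this look took place before 01-May-2020. The efficacy tables still flagged in SAP Table 3 are by-treatment MoCA and MDS-UPDRS summaries in the Evaluable and Per Protocol Sets.

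**Per Protocol definition.** SAP Section 5 now requires all 10 doses and Visits 18 and 19 in window, and refers to COVID-19 deviations. SAP Section 4.2 plans interim tests in the Per Protocol Set once about 40 subjects have completed Visit 8. A subject who has reached only Visit 8 cannot meet the current definition, so the rule used at an interim may have differed. The pre-v4.0 definition is not in the documents, and the extent of the refinement is therefore unknown.

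**Share of efficacy output (SAP Table 3)**

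- MoCA, D-KEFS, MDS-UPDRS, CISI-PD and PDQ-39: 5 × 6 = 30 tables.
- SE-ADL: 3. GDS-15: 9. dCDT: 9.
- Clinical-endpoint total: 30 + 3 + 9 + 9 = 51.
- Each endpoint is split equally over the Evaluable, Per Protocol and Complete Sets, so 2/3 × 51 = 34 tables use the two affected sets.
- There are 4 MRI tables, 1 of them Per Protocol: (34 + 1)/(51 + 4) = 35/55 = 64%.

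These counts describe how much output carries the label. They do not measure bias, which cannot be computed from the documents.

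**The case against.** The likeliest explanation is text left unrevised. SAP v2.0 came 19 days before the cut, so the sentence may have been true then. Version 4.0 still cites protocol V4.0 and still describes both interims as future. That accounts for the error, but the sentence remains wrong in the version that governs the final analysis.

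Safeguards were planned. Protocol 10.6.1 assigns the interims to unblinded statisticians outside the study team, and SAP 4.2 to someone other than the plan's author, with aggregate output only. For MoCA and MDS-UPDRS, the flagged shells test change within each arm, and no between-arm model is flagged. CDR-CCB output falls under a separate plan. This limits what was seen, although side-by-side arm means are still unblinded descriptive results.

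The changes may also be legitimate. COVID-19 is a reason unrelated to results for at least part of the Per Protocol change. Protocol 10.3 leaves the Per Protocol exclusions to the SAP, and v4.0 may well meet the Protocol 10.1 requirement to finalize before database lock and unblinding of the study data. No lock date is given and no breach is shown. No reason is given for the Complete Set.

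Three stronger readings are tempting and are not supported:

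- **That the sets were shaped by the results.** Nothing shows that those who set the v4.0 definitions saw by-arm output.
- **That the sponsor's blinding was contradicted.** Protocol 10.6.1 and SAP 3.6 blind the sponsor to subjects' treatment allocation. Review of aggregate safety data is compatible with that.
- **That a reader cannot tell what was pre-specified.** The Document History dates both set changes, and Protocol 10.4.7 dates the safety interim. A careful reader can reconstruct the order, but Sections 1, 4.2 and 10 do not state it.

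**Conclusion.** The point holds as a false timing statement with a labelling consequence. It is certain, from the stated dates, that the refined Per Protocol Set and the Complete Set post-date unblinded by-arm safety results, taking the safety interim to have been tabulated by treatment as planned. It is probable that they also post-date by-arm efficacy summaries; that rests on one past-tense history entry.

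The two sets supply 34 of 51 clinical-endpoint tables (35 of 55 with MRI). Only secondary efficacy analyses are touched, and the trial is not powered for them. The primary analysis uses the Safety Set, whose definition was not part of the v4.0 change. The finding alleges neither misuse of interim data nor any particular bias. It says that p-values from these two sets should not be presented as pre-specified.

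**What to change.** 1. Correct the Section 1 sentence by version, saying which SAP versions preceded which interim, and update Section 4.2 with the actual interim dates and numbers.
2. List the Per Protocol refinement and the Complete Set in Section 10, each with its reason.
3. Treat the Evaluable Set as the main efficacy set and state which wording applies. Protocol 10.3 (v5.0) requires a diagnosis of PD and cognitive impairment per the inclusion criteria; SAP Section 5 omits this. That criterion itself entered the protocol after the safety interim.
4. Label every refined Per Protocol and Complete Set result as defined after unblinded interim results.
5. Report the Per Protocol analysis once more under the pre-v4.0 definition, as a sensitivity analysis.
6. State who had access to by-arm interim output and whether they took part in setting the v4.0 definitions.

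The cost is SAP wording, table labels, an access statement and one extra Per Protocol run. No new data are needed.
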